Study Design	
This is an initial pilot and feasibility study using a Sequential, Multiple Assignment, Randomized Trial (SMART) design to identify acceptable and effective dietary strategies to optimize both glycemic control and weight management. This pilot study will be done at UNC and Stanford.
 
Sequential randomization will occur following the baseline, 3 months, and 6 months. Following the baseline data collection and a short run-in period, participants will be randomized to one of the three diets (stratified by site with block size of 4). Using a priori decision rules following the 3 and 6 month visit post-initial randomization, those for whom the diet assigned is not acceptable or is not effective will be re-randomized. A total follow-up time of 10.5 months allows for evaluation of the effect of the diets on initial weight loss and on early maintenance of initial weight loss. The decision criteria for re-randomization will incorporate both clinical outcomes (glycemic control and weight change) and acceptability of the diet to the participant.

Subject Population Key Criteria for Inclusion and Exclusion	
Inclusion Criteria
 
 
1. Individuals ages 19-30 years old
 
2. History of type 1 diabetes for greater than one year
 
3. HbA1C less than 13% within the last 6 mos.
 
4. BMI of 27-39.9 at time of phone screening
 
 
Exclusion Criteria
 
The study will exclude based on the following criteria:
 
 
1. Individuals with other metabolic disorders, diagnosed eating disorder, prohibitive strict dietary restrictions, or those with other serious condition that renders participation inappropriate.
 
2. Individuals that have experienced DKA or severe hypoglycemia requiring outside assistance in the last 6 months.
 
3. Females who are pregnant, breast feeding, planning to become pregnant during the study period or delivered a baby in the last 12 months
 
4. Individuals unwilling to follow any of the three study diets.
 
5. Individuals who are unwilling to monitor blood glucose at least three times a day.
 
6. Individuals who have lost 10 or more pounds in the last 6 months.
 

Number of Randomized Subjects	
84 randomized subjects (42 at UNC, 42 at Stanford) Participants withdrawn from the study before randomization will be replaced.

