### **Exclusion criteria**

The following individuals will be excluded from study participation: individuals with other serious metabolic disorders that would render participation unwise, diagnosed eating disorder, or those with other serious conditions that renders participation inappropriate. Individuals who have experienced DKA or severe hypoglycemia requiring outside assistance in the past 6 months will be excluded. Females who are currently pregnant, breastfeeding, planning to become pregnant during the study period or who have delivered a baby in the last 12 months will be excluded. Individuals who are unwilling to follow any of the three study diets will be excluded. Individuals who are unwilling to self-monitor blood glucose levels at least three times a day will be excluded. Individuals who have lost 10 or more pounds in the last 6 months will be excluded.

Medical records will be used to identify patients who potentially meet the eligibility criteria for this study. Medical records will also be used to collect information related to the participant's diabetes care, as well as demographic information. For individuals contacting us about study participation, medical record review will not be required; instead, we will rely on self-report of relevant screening criteria.

Participants may reach out to us after seeing the study on Join the Conquest or through another Type 1 diabetes support network. We will work with NC TraCS to establish recruitment through MyChart.

***Strategies to Optimize Recruitment and Retention:*** Study staff at UNC-CH and Stanford will be responsible for local recruitment activities. Recruitment will use a combination of targeted mailings/emails with phone follow-up and in-person clinic-based strategies. Our recruitment process will utilize the highly successful two-step recruitment strategy used in the FLEX study, consisting of sending an informative recruitment letter/email to eligible participants and following with a series of phone calls by research staff.

***COVID-19 VIRTUAL VISIT TRANSITION (4/2020)*** - All recruitment of new subjects will be conducted electronically. The protocol has been altered to reflect this.

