Additionally, participants will be queried regarding occurrence of both non-severe and severe hypoglycemia by their RD at each encounter (check-in and longer remote sessions). Participants will also be queried regarding increased hypoglycemia on the short and long diet acceptability forms, completed between and at measurement visits. Consistent with a recent report on consensus guidelines for the use of continuous glucose monitoring, contributed to by MPI [name], we define hypoglycemia as CGM-based glucose <70mg/dl for more than 10 min, not requiring help from another person.

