## COVID-19 Provisions-Virtual Visits

MEASUREMENT	Baseline Blood Draw Volume	Remaining Visits Blood Draw Volume
Hemoglobin A1c	2 ml	2 ml

For the SMART pilot, the interventionists (Registered Dietitians) and study physicians will communicate regularly (verbally and in writing per protocol) regarding glucose control so that any changes in medical management can be made in a timely fashion, as it is understood that with weight loss, adjustments in medical management will be needed.

Study personnel will be trained to identify the signs and symptoms of a blood glucose level that is low or high. They will also be trained to check the blood glucose level, using a glucometer. If low blood glucose occurs during a study visit (< 70 mg/dL), study personnel will be trained to administer 15 grams of an oral carbohydrate, and to repeat as needed every 15 minutes until the blood glucose level is > 70 mg/dL. If the blood glucose level is above 300 mg/dL during a study visit, study personnel will be trained to check for urinary ketones. In cases of low or high glucose levels (with or without the presence of ketones), additional medical interventions may sometimes be

needed. Local policies dictate these procedures, which may include a one-time adjustment in the dose of insulin taken and/or the administration of glucose gel, glucagon, or intravenous glucose. If participants experience hypoglycemia or hyperglycemia outside of study visits, they will be advised to treat these situations per their usual diabetes care plan.

***COVID-19 Virtual Visit Provisions:*** *We are no longer asking participants to report their blood sugar or whether or not they have had anything to eat in the last 8 hours. The only fields of the ‘specimen collection form’ that we will complete are those that pertain to the HbA1c collection, that is, time and date of collection along with any problems the participant may have had.*

At each study visit and RD check-in call, hypoglycemia events will be reviewed with the participant. Participants will be asked to notify the study team within 48 hours of any severe hypoglycemic event (seizure, coma, or need for glucagon administration).

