### **Adverse Events**

For purposes of monitoring and reporting adverse events, the following NIH definitions will be used:

**Adverse Event (AE):** any unanticipated, untoward medical occurrence that may present itself during treatment or administration of an intervention, and which may or may not have a causal relationship with the treatment. Adverse events could arise from the study (e.g., breach of confidentiality) or could arise due to the population under study.

**Serious Adverse Event (SAE):** Any medical occurrence that results in death; is life-threatening; requires inpatient hospitalization or prolongation of existing hospitalizations; creates persistent or significant disability/incapacity, or a congenital anomaly/birth defect.

It is highly unlikely that participation in the SMART pilot intervention will cause an AE or SAE. Should an AE occur, however, the study coordinators will immediately report any AE's connected to the study physician at the local site and to the study investigators, who will keep a log of AE's and SAE's. The log will also be used to provide information about AE's in annual progress reports to participating IRBs and NIDDK. Any study participant experiencing hypo/hyperglycemia or an otherwise potentially expected symptom related to diabetes will be encouraged to consult their diabetes care provider or to go to the emergency room immediately as needed.

For monitoring, the coordinators will report AEs to the study MPIs and the overall study project manager ([name]) on a timely basis – 24-48 hours is typical for an SAE, 10-14 days for a routine AE. Local IRB reporting requirements will be followed (rapid

reporting for SAEs only, routine AEs as part of the annual IRB renewal documentation).

All AEs will be reviewed monthly by the study Recruitment, Retention and Data Quality committee, which also serves as the clinical oversight committee in this pilot project, to ensure completeness of documentation and study relatedness. AEs will be reviewed quarterly by the study Steering Committee.

The following grading scale will be used by the Recruitment, Retention and Data Quality committee to adjudicate AE/SAEs. Consensus will be sought among all members and in the event of lack of consensus; this will be noted and reported to the DSMB.

Study Relatedness:	Action Taken:	Status:
1=Definitely Unrelated	0 = None	1 = Resolved
2=Possibly Related	1 = Counteractive Medication	2 = Recovered with minor sequelae

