3=Probably Related	2 = Medical/surgical intervention	3 = Recovered with major sequelae
4=Definitely Related	3 = Hospitalization	4 = Condition still present and under treatment
5=Diabetes Related; Definitely Unrelated	4 = Other (specify under comments)	5 = Condition continues to worsen
		6 = Patient died

All AEs will be reviewed by the study Data and Safety Monitoring Board to determine if an AE is related to the research project. Our team will file a written report to the site IRBs in accordance with local IRB requirements, and to NIDDK. Outcomes for AE's will be monitored by the DSMB and outcome information will be entered into a log for inclusion in reports to participating IRBs and NIDDK as required.

Anticipated events relative to the population under study (e.g., low or high blood glucose) or relative to study activities (e.g., fainting associated with venipuncture) will be noted as potential risks on the informed consent form. The DSMB will also monitor the occurrence of these events. In addition, resource and referral listings for community services will also be provided on a routine basis as needed. Drs. [name] and [name] will also work extensively with the staff at each of the clinics to ensure that if participants need to be referred, these situations are managed in a manner consistent with clinic preferences/policies.

Should any other problems or concerns arise with the data collection or intervention program, the PI or local clinical PI will be available to address these.

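### The 48-hour notification request omits assisted hypoglycemia without seizure, coma or glucagon, so the study team may first hear of such an event about a week later

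*Protocol*

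**What the plan says.** **The urgent request.** Section 12, in the text after the COVID-19 blood-volume table, asks participants to "notify the study team within 48 hours of any severe hypoglycemic event (seizure, coma, or need for glucagon administration"). The bracket has no wording to mark the three items as examples, so it reads as a complete list.

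**The line used at entry.** The Synopsis excludes "Individuals that have experienced DKA or severe hypoglycemia requiring outside assistance in the last 6 months", and Section 5 repeats this: "Individuals who have experienced DKA or severe hypoglycemia requiring outside assistance in the past 6 months will be excluded".

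**The line in the outcome section.** Section 8a says "we define hypoglycemia as CGM-based glucose <70mg/dl for more than 10 min, not requiring help from another person". It also separates two grades of event: "participants will be queried regarding occurrence of both non-severe and severe hypoglycemia by their RD at each encounter".

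**What happens to events outside visits.** Section 12 says of participants that "they will be advised to treat these situations per their usual diabetes care plan". Section 14 adds that they "will be encouraged to consult their diabetes care provider or to go to the emergency room immediately as needed". The Synopsis and Section 12 also have hypoglycemia reviewed at study visits and dietitian contacts. Of anticipated events, low glucose among them, Section 14 says: "The DSMB will also monitor the occurrence of these events".

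The SAP does not address event notification.

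**The concern.** The same kind of event is handled differently before and after enrollment. If a partner had to give juice to a person too confused to self-treat, that person is kept out of the trial for six months. If it happens during the trial, the participant is not asked to tell the study team before the next contact, because there was no seizure, coma or glucagon. No other passage makes such a request. The reporting clocks in Section 14 run from coordinators to the investigators and start only when staff already know.

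This matters because the trial changes the diets of insulin-treated people, restricting calories on two of the diets and carbohydrate on one. Section 12 expects medical management to need adjusting as weight falls and wants changes made promptly. The Synopsis has dietitians and the study endocrinologist work together on insulin dosing. Section 6 lets the investigator withdraw a participant who has trouble controlling glucose. An assisted event is a direct signal for each of these, and the team cannot act on it until it knows.

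**Working it through.** The protocol states no delay figure, so there is none to reproduce. The check is how long an assisted event outside the list can wait for the next scheduled contact.

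**Inputs (Appendix 1, Study Timeline), from Day 0.** Contacts at days 0, 7 and 14; then months 1, 1.5, 2, 2.5, 3 (Measurement Visit 2), 3.5; 3 months + 3 weeks; months 4, 4.5, 5, 5.5, 6, 6.5 (Measurement Visit 3), 7; 7 months + 1 week; months 7.5, 8, 8.5, 9, 9.5, 10 (Measurement Visit 4), 10.5. That is 25 contacts and 24 intervals. All visits and all dietitian sessions count as contacts, following the Synopsis and Section 8a.

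**Assumptions.** The documents do not say how many days a month has, so I use 28 to 31, with 365.25/12 = 30.44 as the middle case. Every contact is kept, and the event is equally likely at any time.

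**Formulas.** With interval lengths L, mean wait = ΣL² / (2ΣL), and maximum wait = the largest L.

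*28-day month.* 18 intervals of 14 days and 6 of 7 days. ΣL = 252 + 42 = 294. ΣL² = 18 × 196 + 6 × 49 = 3,822. Mean = 3,822/588 = **6.5 days**; maximum **14.0 days**.

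*30.44-day month.* 17 intervals of 15.2 days, one of 16.4 (2 weeks to 1 month: 30.4 − 14), and six short ones (7.0, 7.0, 5.8, 9.4, 7.0, 8.2). ΣL = 319.6; ΣL² = 4,544.6 (unrounded lengths). Mean = 4,544.6/639.2 = **7.1 days**; median 6.7; maximum **16.4 days**. The wait exceeds 48 hours for (319.6 − 24 × 2)/319.6 = 85% of follow-up, 7 days for 48%, and 14 days for 7.2%.

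*31-day month.* 17 intervals of 15.5 days, one of 17, and six short ones (7, 7, 5.5, 10, 7, 8.5). ΣL = 325.5; ΣL² = 4,084.25 + 289 + 349.5 = 4,722.75. Mean = 4,722.75/651 = **7.3 days**; maximum **17.0 days**.

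**Sensitivity (30.44-day month).**
- One missed contact: the maximum becomes 16.4 + 15.2 = 31.7 days (unrounded 31.66).
- Counting only visits and check-in calls, as Section 12 literally words it: also 31.7 days.
- During a COVID-19 hold, the Version 6 modification notes describe check-ins every other week, giving a maximum of 14 days.

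**Which responses are delayed.** Section 7 ties diet reassignment and calorie recalculation to Measurement Visits 2 and 3, so earlier notice would not bring either forward. Insulin and medical management advice (Synopsis, Section 12) and discretionary withdrawal (Section 6) have no fixed date and can start only once the event is known.

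**The case against.** The strongest reply is that the passages serve different purposes. One sets eligibility, one defines a CGM outcome, and one sets an urgent report that participants start themselves. Seizure, coma and glucagon are discrete events that a participant can recognize without judgement, whereas needing help is a matter of degree. This stands to the extent that a reader should not infer a contradiction. A narrower urgent tier can be deliberate, the entry criterion can be read as a restriction instead of a definition, and Section 8a never defines severe. But the protocol gives no reason for the narrower tier, and nothing shows that it works better.

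A reader might also infer that assisted events go untreated or unrecorded. The documents say otherwise: participants follow their usual care plan, are directed to their provider or the emergency room as needed, and are asked about hypoglycemia at each visit and dietitian contact, and the DSMB monitors low-glucose events. The Synopsis also has dietitians and the study endocrinologist in regular contact over self-monitored glucose, which may reveal a problem sooner, although its timing is not given.

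Finally, the consent form, diet materials, dietitian query form and staff alert values are not in the documents reviewed. The consent form in particular could carry a broader instruction. That limits certainty about what participants were told, but it does not change what Section 12 asks.

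**Conclusion.** The point holds as a minor, inexpensive improvement. An assisted event without seizure, coma or glucagon falls outside the 48-hour request and is first asked about at the next contact: about 7 days later on average (6.5 to 7.3) and at most 14 to 17 days, with all contacts kept. Participants may report sooner unprompted.

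Two stronger readings should be avoided. The upper figure is not a typical delay: at 30.44 days per month it arises in one interval per participant, for an event just after a contact, and with 28-day months no wait exceeds 14 days. Nor does the delay hold up a change of diet or calorie goal, for the Section 7 reason above.

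The documents give no rate of assisted events, so the number of participants affected could be zero. No endpoint, analysis or result changes. Recruitment stopped with Version 8, so the main value lies in the efficacy trial that this pilot is to inform.

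**What to change.** In Section 12, change the bracketed list to: *seizure, coma, need for glucagon administration, or need for help from another person*. In Section 8a, state that an event requiring help from another person is severe. Carry the same wording into participant materials and the efficacy trial protocol. The limit requested for assisted events then falls from the next scheduled contact (at most 14 to 17 days) to 2 days.

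If the narrower trigger is intended, say so in Section 12 and give the reason. If the query form and alert values already use the assisted line, they need no change.

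The cost is one phrase, one clause, and somewhat more 48-hour notifications.

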***COVID-19 VIRTUAL VISIT TRANSITION (4/2020) DXA discontinued.***

There may be unknown or unforeseen risks associated with study participation.

### **13. Risk/Benefit Analysis**

Participation in this research study may help to improve glycemic control and weight in some participants.

#### **Potential Benefits of the Proposed Research to Human Subjects and Others**

The proposed research may lead to potential benefits for individuals with diabetes, including improved weight and improved diabetes control, and reduced risk of both short- and long-term complications. The risks to participants are reasonable in relation to the anticipated benefits to participants and others because: the risks are judged to be minimal and unlikely, safeguards against these risks are in place, and the potential benefits are important, both to individuals who participate in the study and to the broader population of young adults with T1D.

## Importance of the Knowledge to be Gained

This study should yield new information contributing to the self-management of diabetes, including both weight management and glycemic control, through the use of diet and related behavioral strategies to promote adherence. This knowledge may lead to better care for young adults with diabetes. The development of a feasible and effective novel intervention for young adults with T1D far outweighs potential risk of harm.

## 14. Data Safety & Monitoring:

We will convene a 4-member Data and Safety Monitoring Board to meet twice yearly via video conference call. DSMB members will represent expertise in endocrinology, nutrition, health psychology and behavior change, and study design and statistical analysis relevant to SMART designs. Drs. [name], [name] and [name] will represent the ACT1ON consortium in interactions with the DSMB. The DSMB will review the final study protocol and any significant changes to the protocol over the course of the study especially as related to participant burden or safety. The DSMB will monitor and advise on study participant accrual and retention, progress and completeness for all standardized measurement visits and attendance at intervention sessions. Data quality will be reviewed and staff training and certification will be monitored. Adverse events will be monitored. A summary of the DSMB report will be sent to both the local site IRBs and NIDDK as part of the annual progress reports. Members of the DSMB have been identified and each individual listed below by area of scientific expertise (all with relevant expertise applied to T1D) has agreed to serve:

Endocrinology: [name] MD, University of Washington

Nutrition: [name] PhD RD, University of Cincinnati

Health Psychology and Behavior Change: [name], University of Cincinnati

Study Design and Statistical Analysis: [name], Wake Forest University

### Data Monitoring

Questionnaires will be administered to participants. Data will also be obtained via physical exam and biological specimen collection, as well as data collected based on structured interviewing of intervention acceptability. All aspects of data collection and data storage will be carefully monitored to ensure rapid detection of errors, inconsistencies or other problems. Data are reviewed systematically on a monthly basis throughout the data collection period so that data cleaning will happen close to "real time". The data collectors will follow a strict written protocol that describes study measures and details for conducting measures accurately and in a manner that protects data privacy. They will explain to each participant that s/he has the right to refuse to participate or to refuse to answer any individual question that s/he finds objectionable and emphasize the importance of telling the truth. All institutions associated with this application are experienced in training data collection fieldwork personnel how to handle, store, and process sensitive and confidential data. Certain routine administrative, personnel, physical security, information management, and

computer system or network security practices are always in place. These practices include: building an audio-tape vault security, non-disclosure pledges, and account/keyword security on computer networks. In addition, we take multiple project-specific steps to protect subjects from the risk of a breach in confidentiality. All data will be collected using study identification numbers. The list that links identification numbers to names will be kept in a password-protected file that is accessible only to authorized staff at the respective clinical sites. Only aggregate data that cannot be used to identify individuals will be included in any reports released to other agencies or for publication.

Recruitment and retention will be monitored internally by the study via the study Recruitment, Retention, and Data Quality Committee, using the report templates established for the FLEX trial that show monthly participant recruitment and randomization accrual by site and overall. Reports also detail attendance at each of the intervention sessions and at each of the standardized measurement visits. Any participants permanently withdrawn from the study are documented, including reason for withdrawal. Reports also provide information on completeness of data collection as well as distribution of key variables (e.g., weight, height) for data quality checks. Internally, these reports will be reviewed monthly, and the DSMB will review the reports when they convene twice yearly.

